3.3.2.1. Enoxaparin

Enoxaparin is approved for the prevention of VTE after TKA in the countries in which the trial will be conducted ([Inhixa \[Summary of Product Characteristics\], 2021](#)) ([Lovenox \[Product Monograph\], 2021](#)) In this study, enoxaparin is being administered at the dose recommended by the EU summary of product characteristics (SmPC). While the 40 mg once daily dose is not approved in Canada, it is included as an acceptable regimen in a clinical guide issued by a Canadian vascular medicine professional organization ([Thrombosis Canada, 2013](#)) and has been used in several recent similar trials ([Weitz, 2020](#)) ([Weitz, 2021](#)). Once daily dosing is also expected to improve compliance with dosing. There are no additional benefits and risks to participants apart

from those described in the approved prescribing information for enoxaparin. See Section 3.2.1 for information on the rationale for inclusion of enoxaparin.

3.3.2.2. Apixaban

Apixaban is approved for the prevention of VTE after TKA in the countries in which the trial will be conducted ([Eliquis \[Summary of Product Characteristics\], 2021](#)) ([Eliquis \[Product Monograph\], 2019](#)). In this study, apixaban is being administered at the recommended dose within the approved indication. There are no additional benefits and risks to participants apart from those described in the approved prescribing information for apixaban. See Section 3.2.1 for information on the rationale for inclusion of apixaban.

4. ENDPOINTS

4.1. Primary and Secondary Endpoints

4.1.1. Primary Endpoint

The primary endpoint is the incidence of confirmed, adjudicated VTE (defined in Section 5.2.1) through day 12 (REGN9933 vs enoxaparin).

4.1.2. Secondary Endpoints

The secondary endpoints are:

- Incidence of major bleeding and CRNM bleeding (defined in Section 5.3.1) through time of venography (or day 12, whichever is earlier)
- Incidence of treatment-emergent adverse events (TEAEs) through the end of study
- Incidence of major VTE (defined in Section 5.2.2) through day 12 (REGN9933 versus enoxaparin)
- Incidence of DVT as measured by venography of the operated leg on day 10 ± 2 days (REGN9933 vs enoxaparin)
- Concentrations of REGN9933 in serum through end of study
- Change in aPTT from baseline through end of study
- Change in PT from baseline through end of study
- Incidence and titer of anti-drug antibodies (ADA) to REGN9933 through end of study
- Incidence of confirmed, adjudicated VTE through day 12 (enoxaparin vs apixaban)

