8.2. Rescue Treatments

8.2.1. Treatment of VTE

Treatment of symptomatic VTE events that occur during the trial will be managed by the investigator per local practice.

For participants receiving either enoxaparin or apixaban, increasing the dose of either agent to therapeutic levels (according to local standards) may be considered. For participants who develop a symptomatic VTE after receiving REGN9933, consideration may be given to DOACs, which have more predictable anticoagulant activity and lower bleeding liability than other anticoagulants. Therapeutic doses of LMWH may also be considered.

Asymptomatic VTE may be monitored with additional imaging assessments at the discretion of the site investigator. In addition, treatment with therapeutic anticoagulation may be considered, depending on the clinical situation, and at the discretion of the site investigator.

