8.8.1. Prohibited Medications and Procedures

Administration of enoxaparin prior to TKA surgery is prohibited (Section 7.2.2 Exclusion criterion 10).

Anti-platelet therapy (except low doses of ASA ≤ 100 mg/day) is prohibited, unless indicated for treatment of an AE.

The following procedures/devices are prohibited after study drug has started:

- Use of spinal or epidural analgesia post-operatively
- Pneumatic compression devices

Subjects are prohibited from donating blood products through the EOS visit. Subjects are prohibited from donating sperm through the EOS visit. Subjects are prohibited from having planned, elective surgeries (except for TKA performed on day 1) through the EOS visit.

For patients assigned to the REGN9933 treatment arm, anticoagulant medications (including, but not limited to, vitamin K antagonists, heparins, DOACs) are prohibited after study drug has been started, unless they are indicated for treatment of an AE.

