10. SAFETY EVALUATION AND REPORTING

10.1. Recording and Reporting Adverse Events

10.1.1. General Guidelines

The investigator must promptly record all clinical events occurring during the study data collection, from the time of signing the ICF to the end of study (see Section 11.4.5.1). Medical conditions that existed or were diagnosed prior to the signing of the Informed Consent will be recorded as part of medical history. Abnormal laboratory values and vital signs observed at the time of Informed Consent should also be recorded as medical history. Any subsequent worsening (ie, any clinically significant change in frequency and/or intensity) of a pre-existing condition that is temporally associated with the use of the study drug should also be recorded as an AE.

At each visit, the investigator will determine whether any AEs have occurred by evaluating the participant. Adverse events may be directly observed, reported spontaneously by the participant, or by questioning the participant at each study visit. Participants should be questioned in a general way, without asking about the occurrence of any specific symptoms. The Investigator must assess all AEs to determine seriousness, severity, and causality, in accordance with the definitions in Section 10.2. The Investigator's assessment must be clearly documented in the site's source documentation with the Investigator's signature. The Investigator should follow up on SAEs (and AESIs) until they have resolved or are considered clinically stable; AEs should be followed until they are resolved or last study visit, whichever comes first.

Always report the diagnosis as the AE or SAE term. When a diagnosis is unavailable, report the primary sign or symptom as the AE or SAE term with additional details included in the narrative until the diagnosis becomes available. If the signs and symptoms are distinct and do not suggest a common diagnosis, report them as individual entries of AE or SAE.

Laboratory results, vital signs, and other diagnostic results or findings should be appraised by the Investigator to determine their clinical significance. Isolated abnormal laboratory results, vital sign findings, or other diagnostic findings (ie, not part of a reported diagnosis) should be reported as AEs if they are symptomatic, lead to study drug discontinuation, dose reduction, require corrective treatment, or constitute an AE in the investigator's clinical judgment.

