10.2. Definitions

10.2.1. Adverse Event

An AE is any untoward medical occurrence in a participant administered a study drug which may or may not have a causal relationship with the study drug. Therefore, an AE is any unfavorable and unintended sign (including abnormal laboratory finding), symptom, or disease which is temporally associated with the use of a study drug, whether or not considered related to the study drug (ICH, 1994).

For studies with patient reported outcomes (PRO), the PRO data are generally not reportable as individual AEs and thus will not be reported or reconciled as such.

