5.8.1. Analysis of Adverse Events

AE incidence tables will be presented for each treatment group, including the number (n) and percentage (%) of participants experiencing an AE, where multiple instances of the same event

occur in the same participant the event will be counted only once for that participant. The denominator for computation of percentages is the number of participants in each treatment group.

Treatment Emergent Adverse Events (TEAEs) are defined as AEs with either initial onset after the first dose of study treatment or that worsen after the first dose of study treatment. The number and proportion of participants reporting TEAEs will be summarized by SOC and PT.

Overall TEAE summary

The overall summary of TEAEs will be provided with number and proportions of participants with any:

- TEAEs
- Treatment-emergent serious adverse events (TE-SAEs)
- TEAEs of special interest (TE-AESI)
- Summary of deaths

TEAE incidence

Number and proportions of participants reporting TEAEs will be summarized for the following TEAEs:

- TEAEs
 - TEAEs by primary SOC and PT
 - TEAEs by primary SOC, PT and severity
 - TEAEs related to study drug by primary SOC and PT
 - Treatment-related TEAEs by primary SOC, PT and maximum severity
 - TE-AESI by primary SOC and PT
 - TEAEs leading to permanent treatment withdrawal by primary SOC and PT
- TE-SAEs
 - TE-SAEs by SOC and PT
 - Treatment-related TE-SAEs by primary SOC and PT
- TEAEs leading to death by primary SOC and PT

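### The TEAE totals can include investigator-reported VTE, with no version that leaves it out, so lack of efficacy and tolerability are mixed in an unpredictable direction

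*Protocol*

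**What the plan says.** Protocol 4.1.2 lists "Incidence of treatment-emergent adverse events (TEAEs) through the end of study" among the secondary endpoints. It is the natural measure for the Protocol 2.2 objective on overall safety and tolerability.

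Protocol 10.2.1 defines an adverse event broadly: "An AE is any untoward medical occurrence in a participant administered a study drug which may or may not have a causal relationship". The one exception there concerns patient-reported outcomes: "the PRO data are generally not reportable as individual AEs". Protocol 10.1.1 asks the investigator to record every clinical event up to the end of the study. It also says that isolated diagnostic findings "should be reported as AEs if they are symptomatic, lead to study drug discontinuation, dose reduction, require corrective treatment, or constitute an AE". The last of these criteria is a matter of clinical judgement for the investigator.

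On asymptomatic VTE, Protocol 8.2.1 says: "Asymptomatic VTE may be monitored with additional imaging assessments at the discretion of the site investigator". It leaves therapeutic anticoagulation to the same discretion. For the REGN9933 arm only, Protocol 8.8.1 says that anticoagulants "are prohibited after study drug has been started, unless they are indicated for treatment of an AE". Under Protocol 8.8.2 the comparator arms may continue prophylaxis after the protocol-defined treatment.

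Bleeding has an explicit instruction that every event be entered as an AE (Protocol 9.2.3.6). VTE has none.

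SAP 5.8.1 defines TEAEs as "AEs with either initial onset after the first dose of study treatment" or that worsen after it. The section lists overall, serious, related and severity summaries, and none of them excludes VTE.

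**The concern.** In a prophylaxis trial, a VTE is a failure of the drug to do its job. If the same event also enters the tolerability count, a difference in TEAE incidence cannot be read as a difference in harm.

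The overlap is also poorly controlled. Protocol 3.3.1 reports that fewer than 15% of VTEs in the earlier factor XI trials were symptomatic, so most VTE here will probably be asymptomatic DVT found on venography. If such a DVT is handled as an isolated finding, it becomes an AE when it is treated or when the investigator calls it one. The investigator knows the arm. The blinded committee classifies VTE and bleeding (Protocol 6.3.3), but no passage has it decide AE entry.

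Protocol 3.2.1 applies the relevant principle elsewhere: it leaves minimal bleeding out of the secondary safety endpoint because its criteria are unclear and treatment is unblinded. AE entry of asymptomatic DVT has the same weakness, yet it feeds a secondary safety endpoint.

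**Working it through.** The documents give no TEAE rate, so there is no planned figure to reproduce. The check asks how far VTE alone can move the TEAE totals.

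**Inputs from the documents.** VTE rate v = 22.4% for enoxaparin and 13% for REGN9933, with about 120 participants per arm (Protocol 11.2). Expected VTEs are 120 × 0.224 = 26.9 and 120 × 0.13 = 15.6, a gap of 11.3 participants or 9.4 points.

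**Assumptions.** q is the share of participants with some other TEAE, equal in both arms. r is the share of VTE recorded as an AE. VTE and other TEAEs are independent. The planning rates are for confirmed VTE, whereas TEAEs run to day 75 in the safety set, so v is an approximation.

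**Equal recording.** TEAE incidence in an arm is 1 − (1 − q)(1 − r·v). Enoxaparin minus REGN9933 is then (1 − q) × r × 9.4 points:

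| r | q = 40% | q = 60% | q = 80% |
|---|---|---|---|
| 100% | 5.6 | 3.8 | 1.9 |
| 50% | 2.8 | 1.9 | 0.9 |
| 15% | 0.8 | 0.6 | 0.3 |

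For example, at q = 60% and r = 100% the difference is 0.4 × 9.4 = 3.8 points (69.0% against 65.2%). The 15% row approximates the case where only symptomatic VTE is recorded.

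**Unequal recording.** The difference becomes (1 − q)(r_E × 22.4 − r_R × 13), where r_E and r_R are the enoxaparin and REGN9933 shares. It is zero when r_E / r_R = 13 / 22.4 = 0.58, and negative below that.
- r_R = 100%, r_E = 50%, q = 60%: 0.4 × (11.2 − 13) = −0.7, so REGN9933 shows 0.7 points more TEAEs.
- r_R = 50%, r_E = 80%, q = 60%: 0.4 × (17.92 − 6.5) = +4.6, so REGN9933 shows 4.6 points fewer.

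**Can a reader subtract the VTE rows?** Take q = 60% and r = 100%, where the rate without VTE is 60% in both arms. Subtracting VTE from the any-TEAE totals gives 69.0 − 22.4 = 46.6% for enoxaparin and 65.2 − 13 = 52.2% for REGN9933. That is a false 5.6-point difference in the opposite direction, because participants with both kinds of event are removed. A correct total needs participant-level recounting.

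**After the change.** In a summary that excludes VTE terms, the VTE-driven difference is zero by construction.

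**The case against.** Much of the opposing case is sound.

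- A reader might infer that the TEAE endpoint contains the primary endpoint. It does not. The primary endpoint is adjudicated, runs through day 12 and uses the mITT set as randomized. TEAEs are investigator-reported, run to the end of the study and use the safety set as treated. The two overlap.
- A reader might infer that an effective drug will necessarily look better tolerated. That needs both efficacy and similar recording across arms. Protocol 8.8.1 gives sites a reason, in the REGN9933 arm only, to label a treated DVT as an AE, which pushes the other way.
- A reader might infer that the site's own reading of the venogram drives AE entry. No passage says so, and Protocol 9.2.2.2 sends all images for central reading.
- The discretionary rule covers findings that are not part of a reported diagnosis, and Protocol 10.1.1 also says to report diagnoses. A confirmed DVT can be read as a diagnosis and so as reportable. The event-reporting manual, which is not available here, may settle this. The protocol text does not.
- The TEAE tables are by SOC and preferred term, so VTE appears in its own rows. The AE analysis is descriptive, the objective names no comparator, and the IDMC considers VTE and TEAEs as separate items (Protocol 6.1.1.1). These points limit the consequence. They do not supply de-duplicated totals without VTE, and they do not correct unequal recording.

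**Conclusion.** The concern holds as a question of interpretability. VTE is not exempt from AE recording, there is no VTE-specific recording rule, and no total in SAP 5.8.1 leaves VTE out.

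Under equal recording the distortion of overall TEAE incidence ranges from 0.3 points (q = 80%, r = 15%) to 5.6 points (q = 40%, r = 100%). It cannot exceed 9.4 points even if no one has another TEAE. Under unequal recording it can take either sign. All of this rests on the planning VTE rates, on independence, and on values of q and r that the documents do not supply. Participants in the safety set without an evaluable venogram would reduce the VTE available to be recorded.

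The primary and adjudicated bleeding analyses are unaffected. This is an inexpensive improvement to a secondary safety endpoint.

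**What to change.** 1. In SAP 5.8.1 keep the all-TEAE tables as they are. Add the overall TEAE, TE-SAE, related and severity summaries excluding a fixed list of VTE preferred terms, set before database lock. Use the excluded version to describe tolerability beyond VTE.
2. Add a listing that reconciles site-reported VTE adverse events with the adjudication committee's classification.
3. State in Protocol 10.1.1 one AE-recording rule for VTE, covering asymptomatic venographic DVT and applying identically to all arms.

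VTE should not be removed from the all-TEAE tables or confined to the efficacy tables. Protocol 3.3.1 acknowledges that there is no clinical evidence yet that REGN9933 prevents post-surgical VTE, so failure to prevent it is itself a risk to participants.

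The cost is a term list, a second run of existing tables, one listing and a wording clarification. The table filter removes unequal VTE recording from the excluded totals only. The all-TEAE totals still need the common recording rule.

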4.1.3. Exploratory Endpoints

The exploratory endpoints are:

- Incidence of confirmed VTE (defined in Section 5.2.1) through day 12 (REGN9933 vs apixaban) and through the end of study
- Incidence of major VTE (defined in Section 5.2.2) through the end of study
- Incidence of confirmed symptomatic DVT in either leg through day 12 and through the end of the study
- Incidence of confirmed PE through day 12 and through the end of study
- Incidence of fatal PE, which includes sudden death for which PE cannot be ruled out, through day 12 and through the end of study
- Incidence of DVT as measured by venography of the operated leg on day 10 ± 2 days (REGN9933 vs apixaban)
- In participants with DVT detected on venogram:
 - distribution of DVT (proximal versus distal)

- for proximal DVT, size of VTE
- for distal DVT, the number of veins affected
- Incidence of major bleeding and CRNM bleeding (defined in Section [5.3.1](#)) through end of study
- Incidence of minimal bleeding through time of venography and through the end of study
- Change in measures of coagulation pathway function compared to baseline, including, but not limited to:
 - FXI:C ([Factor XI functional activity] FXI coagulant activity assay)
 - Total FXI concentration
 - Thrombin generation assay (TGA) for extrinsic and intrinsic pathways

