2.3. Exploratory Objectives

The exploratory objectives of the study are:

- Explore the efficacy of REGN9933 in prevention of VTE after unilateral TKA through the end of study, compared to enoxaparin and apixaban
- Explore the efficacy of REGN9933 in prevention of symptomatic, clinical thrombosis, compared to enoxaparin and apixaban
- Explore the efficacy of REGN9933 in prevention of DVT detected by venography, compared to apixaban
- Explore the extent of DVT burden on venography in participants receiving REGN9933 compared to enoxaparin and apixaban
- Explore the bleeding risk (ie, major bleeds and CRNM) of REGN9933 after unilateral TKA through end of study compared to enoxaparin and apixaban
- Explore the occurrence of minor bleeding compared to enoxaparin and apixaban

- Explore biomarkers related to FXI inhibition by REGN9933
- Develop a molecular understanding of venous thromboembolism, and related diseases
- Explore relationships between PK, biomarkers of anticoagulant activity, and efficacy
- To study REGN9933 mechanism of action the coagulation cascade, VTE, and related diseases
- Explore whether potential differences in participant efficacy and safety are associated with genotype and gene expression and further study FXI and coagulation-related diseases, using optional whole blood DNA and RNA collected from consented subjects

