11.2. Justification of Sample Size

Up to total of approximately 360 participants will be randomized in a 1:1:1 allocation ratio to REGN9933, apixaban or enoxaparin. Each arm will have an approximate number of 120 participants.

The sample size was determined using the following assumptions:

- The event rate of VTE for REGN9933 was assumed to be 13% and was set to be 22.4% for enoxaparin ([Verhamme, 2021](#)) ([Weitz, 2020](#)).
- The prior distribution of the treatment difference, was assumed to be $\log(OR) \sim N(0, 0.843)$, which was expressed as the log(OR). The prior distribution follows a normal distribution centered around no treatment difference and with a variance such that extreme treatment differences are expected to be unlikely, ie, the probability that OR is between 0.25 and 4 is 90%.

Using these assumptions, and for the purpose of choosing a sample size, the following quantities were simulated:

- The probability of any beneficial effect of REGN9933 over enoxaparin, ie, the posterior distribution of the odds ratio comparing REGN9933 to enoxaparin of confirmed VTE. A beneficial effect is where $OR_{RE} < 1$, and thus the study will estimate $P(OR_{RE} < 1 | \text{data})$.
- In 75% of the simulated trials, in studies where the $P(OR_{RE} < 1 | \text{data}) > 0.95$, the sample size was 120 participants or less. Therefore, a sample size of 120 subjects per group was chosen.

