4.4.2. Secondary Efficacy Variables

- Incidence of major VTE through day 12 (REGN9933 versus enoxaparin). Major VTE includes: proximal DVT; confirmed symptomatic DVT of either leg; confirmed fatal or nonfatal PE including unexplained death for which PE cannot be ruled out
- Incidence of DVT as measured by venography of the operated leg on day 10 ± 2 days (REGN9933 vs enoxaparin)
- Incidence of confirmed, adjudicated VTE through day 12 (exoxaparin vs apixaban)

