5.7. Analysis of Efficacy Variables

The efficacy analyses will be performed using the mITT analysis set.

Pooling of Sites/Centers

For this multi-center study, a small number of participants are anticipated at some sites. Since these study sites may not provide appropriate information to allow the analysis, the efficacy analyses adjusted/stratified by country instead of site will be conducted.

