5.7.2. Analysis of Secondary and Exploratory Efficacy Variables

Unless otherwise specified, categorical efficacy endpoints (defined in Section [4.4.2](#) and Section [4.4.3](#)) will be analyzed by Bayesian logistic regression models in a similar manner for the primary efficacy variable on the mITT set.

Bayesian summary statistics (posterior mean and median, and two-sided 90% credible interval) of the treatment effect (odds ratio) will be reported.

For the exploratory analyses, the distribution of DVT (proximal versus distal) will be summarized descriptively for participants detected on venogram. Proximal DVT will be characterized by the size of the venous thromboembolism (VTE), while distal DVT will be summarized by the number of affected veins.

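### The exploratory between-arm comparison of DVT burden is summarised only in participants with a DVT on venogram, a subset that treatment can change

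*Protocol*

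**What the plan says.** Protocol 2.3 states a between-arm objective: "Explore the extent of DVT burden on venography in participants receiving REGN9933 compared to enoxaparin and apixaban". SAP 1.2 repeats it.

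The endpoints that serve it are in Protocol 4.1.3, under the qualifier "In participants with DVT detected on venogram". They are the proximal/distal distribution, thrombus size where the DVT is proximal, and, in the third item, "for distal DVT, the number of veins affected". SAP 4.4.3 carries the same list and qualifier. SAP 5.7.2 adds that "the distribution of DVT (proximal versus distal) will be summarized descriptively for participants detected on venogram", with size for proximal DVT and vein count for distal DVT. It names no model or contrast for these items.

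Three other provisions bear on the point:

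- SAP 4.4.2 lists "Incidence of major VTE through day 12 (REGN9933 versus enoxaparin). Major VTE includes: proximal DVT", together with symptomatic DVT, PE and unexplained death. Incidence of venographic DVT is also listed, against enoxaparin as a secondary endpoint and against apixaban as an exploratory one.
- SAP 5.7 sets the population for efficacy: "The efficacy analyses will be performed using the mITT analysis set".
- The opening of SAP 5 gives a default for categorical data, under which percentages use the full size of the treatment arm.

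**The concern.** Randomisation makes the arms comparable as randomised. It does not make the participants who went on to have a DVT comparable, because treatment influences who enters that group. If one drug removes the mildest thrombi, those left in its arm are on average more severe, although nobody is worse off. A table of severity among the affected can then point the opposite way to the effect on burden per participant treated.

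The trial is presented as a proof of concept that may inform further development (Protocol 1). A table in which REGN9933 thrombi look more proximal or more extensive could be misread as a signal about the drug. Neither document warns against reading the DVT-positive summaries as a treatment comparison.

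**Working it through.** The documents give no figure for the burden endpoint, so there is none to reproduce. The check illustrates how far the summaries can move at the planning rates.

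**Inputs from the documents.** Protocol 11.2: "The event rate of VTE for REGN9933 was assumed to be 13% and was set to be 22.4% for enoxaparin", and "Each arm will have an approximate number of 120 participants". Treating all VTE as venographic DVT, the expected numbers affected are:

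- Enoxaparin: 0.224 × 120 = 26.9, about 27
- REGN9933: 0.13 × 120 = 15.6, about 16

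**Assumed inputs.** The documents do not give the proximal share *s* of DVTs on enoxaparin; 10% to 30% is used. A loose bracket comes from the placebo figures in Protocol 3.3.1 (13% proximal DVT) and Protocol 1 (over 50% any venous thrombosis): 13/50 = 26% at most, if the two sources are comparable. Vein counts are also assumed.

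**Worked example, only distal clots prevented.** Enoxaparin has 5 proximal and 22 distal. REGN9933 prevents 11 distal, leaving 5 and 11.

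| Quantity | Enoxaparin | REGN9933 |
|---|---|---|
| Proximal share of DVTs | 5/27 = 18.5% | 5/16 = 31.3% |
| Proximal incidence | 5/120 = 4.2% | 5/120 = 4.2% |

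Suppose the 22 distal DVTs are 14 one-vein and 8 three-vein, and the 11 prevented are all one-vein. Total veins are 14×1 + 8×3 = 38 against 3×1 + 8×3 = 27.

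| Mean distal veins | Enoxaparin | REGN9933 |
|---|---|---|
| Per participant with distal DVT | 38/22 = 1.73 | 27/11 = 2.45 |
| Per participant in the arm | 38/120 = 0.32 | 27/120 = 0.23 |

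**Varying the assumed share.** When only distal DVT is prevented, the REGN9933 share is 0.224 × *s* / 0.13. The last column is the percentage of 20,000 simulated trials (multinomial, 120 per arm) in which the REGN9933 share exceeds the enoxaparin share.

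| *s* on enoxaparin | Share on REGN9933 | REGN9933 share higher |
|---|---|---|
| 10% | 17% | 72% |
| 20% | 34% | 83% |
| 30% | 52% | 91% |

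**Proportional prevention.** If proximal and distal DVT fall in the same proportion, the expected share is *s* in both arms. The REGN9933 share is then higher in 47% to 49% of simulated trials, which is chance.

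**All-participant denominator, *s* = 20%.** With only distal DVT prevented, proximal incidence is 0.224 × 0.20 = 4.5% in both arms, so no harm appears. With proportional prevention it is 0.13 × 0.20 = 2.6% on REGN9933 against 4.5%, so the benefit shows.

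The mITT set may be smaller than 120 per arm, and the documents give no evaluability rate, so these counts are upper bounds.

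**The case against.** The strongest reply is that the plan does not look at proximal disease only among the affected. Major VTE contains proximal DVT and is analysed by Bayesian logistic regression in mITT, as is venographic DVT incidence. In the worked example, with no other major events, the planned output would show major VTE 5/120 against 5/120 and DVT 27/120 against 16/120. A careful reader would see fewer DVTs and unchanged proximal disease. This stands, but the view is partial. Major VTE mixes in symptomatic DVT, PE and unexplained death. Protocol 3.3.1 reports symptomatic VTE below 2% in the cited studies (below 0.02 × 120 = 2.4 per arm, if it carries over), so the mixing is probably small. Through day 12 the endpoint is listed only against enoxaparin, while the burden objective also names apixaban. It says nothing about clot size or vein count.

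Second, the SAP 5 default on percentages may already give proximal and distal counts over the whole arm. That also has force. But SAP 5.7.2 restricts the distribution to DVT-positive participants and can be read as overriding the default. The default also does not reach a mean vein count or a thrombus size.

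Third, a reader might infer that REGN9933 will appear to cause more proximal disease. The documents do not support this. It needs selective prevention of small distal clots, and nothing in them says the drug acts that way. For proximal size, the direction depends on which proximal clots are prevented. Participants with DVT or PE confirmed early have no venogram (Protocol 6.1 and 9.2.2.1) and leave the subset, so the net direction is not fixed.

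Finally, the endpoint is exploratory and descriptive, in about 27 and 16 people, and no decision is tied to it. Describing thrombi among those who have them is legitimate. All of this stands.

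**Conclusion.** The mismatch is real and minor. The objective asks about burden in participants receiving each drug; the measures describe thrombi in those who developed one. Under selective prevention of small distal clots, the summaries can show a higher proximal share and more veins per affected participant with no added proximal disease: 18.5% against 31.3% in the example. Under proportional prevention there is no systematic shift, but a DVT-positive table still does not show total burden per arm.

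It would go too far to say that proximal disease is compared only among DVT-positive participants, or that the table must turn against the better drug. The sizes rest on the assumed proximal share, the assumed vein counts and 120 evaluable participants per arm. The structural point rests on the wording of the two documents alone. The primary result is not affected.

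**What to change.** In Protocol 4.1.3 and SAP 4.4.3 and 5.7.2:

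- For the between-arm burden comparison, report ordered categories per arm: no DVT, distal only by number of veins, proximal by size category. Fix the size cut-points before the data are seen.
- Use all mITT participants as the denominator, and state that the SAP 5 total-arm convention applies here. An evaluable-venogram denominator would drop participants whose DVT or PE was confirmed early; mITT keeps them.
- Give participants with DVT or PE confirmed early and no venogram their own category, or count them by confirmed location.
- Prefer categories to a mean proximal size with zeros, which would be 115 zeros out of 120 in the example.
- Keep the DVT-positive table, labelled as a description of thrombi and not a treatment comparison.

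The cost is a small wording change in both documents and one added table from data already collected.
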